3.1 Problem Statement

Growing evidence shows that multilevel systems-based interventions (i.e., those in which the patient, healthcare providers, and clinic systems are all recognized) that are designed to bolster optimal medication adherence can produce significant improvements in patients' medication adherence and clinical outcomes. Our Ayudando a Latinos Hipertensos Para Mejorar Adherencia a sus Medicamentos (ALMA) trial, which informs this study significantly improved both BP control (51% vs. 29%, $p=.04$) and medication adherence (78% vs. 72%, $p=.02$) compared to enhanced usual care in a sample of Latino patients followed in a safety-net practice. The ALMA intervention was a systems-level approach to improving BP control based on the evidence-based teamlet model and included an office system redesign component (e.g., electronic health record (EHR) embedded templates) and a primary care physician (PCP) support (e.g., telehealth MA coaching) component. Despite their efficacy, systems-level interventions like ALMA often takes up to 17 years to be translated into clinical practice. Implementation strategies are sorely needed to accelerate the translation of evidence-based interventions into routine "real world" safety-net practices, to reduce disparities in BP control in vulnerable populations. However, data are scant regarding which strategies effectively facilitate the translation of efficacious interventions into practice in these settings. Moreover, while a central premise of ALMA is that it will build clinic capacity to deliver equitable, high-quality care to health disparity populations followed in primary care clinics, the program was not designed to evaluate the impact of healthcare technologies on patient-provider relationships. While technology has shown great promise in improving the clinical management of hypertension (HTN), its impact on patient-provider relationships is unclear. Some evidence suggests telehealth could strengthen these relationships through improved access to the care team and remote patient monitoring, but its technical and interpersonal drawbacks may reduce commitment and trust. Addressing these risks is vital for clinics that serve vulnerable populations who may have limited technology access and low digital literacy, and consequently feel disenfranchised from providers using telehealth.

3.2 Purpose of Study/Potential Impact

Practice facilitation (PF)—an implementation strategy that can accelerate the translation of evidence-based systems interventions into routine practice—promises to overcome these barriers. PF involves both a role (a facilitator) and a process for supporting primary care practices to build motivation and capacity at the individual, team, and systems levels to improve organizational performance and health outcomes. Practice facilitators are specially trained individuals who work with primary care practices to help healthcare teams develop the skills they need to adapt and implement evidence-based approaches to their practice environment (e.g., by redesigning workflows to support team-based care).

Despite the growing evidence of PF as effective for the implementation of preventive screenings, its impact on implementing evidence-based systems to support HTN management in safety-net practices remains largely untested. Our study provides a unique

opportunity to fill this evidence-to-practice gap by evaluating the effectiveness of PF as a practical and replicable strategy to implement Advancing Long-term Improvements in Hypertension Outcomes through a Team-based Care Approach (ALTA) in a network of safety-net primary care practices that serve a large population of low-income patients.

ALTA is a health systems approach to improving medication adherence and BP control in primary care practices. It is designed to build practice capacity to address the needs of hypertensive patients by utilizing a team-based approach to delivering HTN care. ALTA includes five key components, which are conducted by existing members of the practice (Table 1): (1) Identify ALTA-eligible patients using hypertension registries. (2) Refer ALTA patients to a clinic Health Coach using the EHR. (3) Coach ALTA patients using a structured counseling tool integrated in the EHR to identify patients' treatment goals; assess their current level of BP control and medication adherence; identify barriers and facilitators to medication adherence; develop patient-centered adherence goals and action plans; and use a structured treatment algorithm to optimize patient antihypertensive medication regimen. (4) Document brief progress notes from the coaching session in the EHR to inform other team members of the patient's adherence status, action plans, progress toward goals, and any changes to the antihypertensive medication regimen. (5) Monitor and schedule follow-up sessions with ALTA patients in the EHR.

Table 1. ALTA components

ALTA components	ALTA Activities
Identify and Refer	
 • EHR registry to identify patients with uncontrolled HTN and non-adherent • EHR-based referral to MA/PCA/RN
Coach	
 • Structured assessment of medication adherence • Use of MINT to identify facilitators/barriers to adherence and discuss personalized strategies to improve adherence behaviors • Use of structured medication titration algorithm to optimize patient treatment regimen • Use of teach back to ensure patient understanding of treatment plan • Co-creation of culturally relevant goals and action plans
Document	
 • Structured documentation of coaching sessions in EHR to enable tracking patients' progress over time • EHR Documentation of individualized treatment plan, medication adherence goals, and action plan to guide future sessions and share with primary care provider for clinic visits
Monitor	
 • Consistent monitoring of patient progress through completion of and tracking follow-up sessions with ALTA patients

3.3.1 Potential Benefits

The intervention is expected to benefit the patients by improving their blood pressure control and adherence to antihypertensive medications, reducing their cardiovascular risk profile, and increasing their role as active participants in the management of their HTN. The intervention is expected to benefit the practices, by changing the usual care practices so that a better quality of treatment for HTN is implemented and potentially maintained, and

generalizes to new patients, as well as to other providers. The knowledge gained from this study will provide key academic, community, and policy stakeholders a practical and replicable strategy for implementing efficacious interventions into routine care that has potential for broad dissemination, ultimately contributing to the reduction of health disparities seen in racial and ethnic minority populations.

3.3.2 Potential Risks

Though we expect the level of risk due to this project to be minimal, potential risks may include the following:

Elevated blood pressure: Since this study focuses on reducing BP, all of the patients are required to have uncontrolled HTN to be eligible to participate. All patients will have a primary care provider as part of this study; however, it is quite conceivable that a patient may have elevated BP readings during the study that will require more aggressive management. The clinical care of any given patient will be entirely handled by the patient's primary care provider, and study participants will be made aware of this at the consent visit. Similarly, any medical problem that arises during study visits will be referred to the patient's provider. If at any study visit, BP is elevated >180 SBP or >110 DBP, the participant will be directed to seek medical attention immediately at the clinic. All such participants will be required to bring to the next study visit a signed document attesting that they sought care. The Program Manager will follow-up with the participant's primary care provider to ensure proper medical follow-up. These data will be reviewed periodically by the DSMB and will be reported to the NYU IRB until the end of Year 5.

Violation of participant privacy and confidentiality: Loss of confidentiality is the greatest potential risk to study subjects. We will obtain written consent from all participants (i.e., practice clinical and nonclinical staff and patients) who participate in surveys, interviews, and/or audiotaped health coaching visits; however, no identifying information will be included on the transcripts of interviews or surveys. As part of the process involved in obtaining written informed or verbal consent, all participants will be reminded that their responses are confidential and that they may refuse to participate in the project or withdraw at any time without explanation, and further, that such an action will in no way affect their treatment or future interactions with their physician at the practices. Also, if a participant is uncomfortable during a research encounter, they may stop at any time. All survey data entered into the research database will be protected by confidential entry codes. Names will be replaced with identification numbers. All patient data will be de-identified prior to transfer to subcontracts. Locked file cabinets will be used to store materials with identifying information (e.g., patient consent forms). Only members of the research team will have access to patient's personal information file. Study data will be transmitted to [name] and the data analyst for data processing using only secure methods (e.g., encrypted email). All electronic audiotaped data will be saved on a secure server housed by NYULH and backed up daily or weekly depending upon the receipt of data. PHI will be confined to a secure server that is not connected to the Internet. All computers are password protected and on a private LAN network. No file and database servers are accessible to the public through the Internet. Prior to inclusion in any data set (internal and external), data will be stripped of all

identifying information. Finally, the web-based surveys will be accessed via a HIPAA compliant application. The data collected for this study will be used strictly for the purposes stated in this grant application and will only be available to relevant research staff. IRB approval will be sought prior to any data collection involving human subjects. Finally, all identifiable patient health information will be obtained and managed in accordance with the HIPAA Privacy Rule, 45 CFR Parts 160 and 164.

NYULH employees recruited as research subjects are more vulnerable to undue influence or coercion because of the possibility that they may perceive employment or other benefits as dependent upon their participation in research. In addition, NYULH employees may experience increased risk of invasion of privacy or loss of confidentiality. To minimize these risks, employees who wish to participate will be enrolled by a study team member with no direct supervisory or evaluation responsibilities. At time of enrollment, the study team member will emphasize that participation is voluntary and refusal to participate will not affect employment or job performance evaluation. No identifiable information will be collected from these employees. Employees will be assigned a unique study number that includes neither contact nor identifying information. No linking list will be kept.

Anxiety: There is a potential risk that participants (i.e., practice clinical and nonclinical staff and patients) may feel uncomfortable or anxious during the audiotaped health coaching sessions, and/or semi-structured interviews. To mitigate this potential challenge, the study staff member who conducts the semi-structured interview will be trained to act professionally and address all participants' concerns. Participants will also be reminded that the tapes are only for research purposes and will not influence their relationship with the practice. Moreover, participants will be reassured that the tapes will be saved in a secure and confidential database that only the study staff will have access to, and that have the right to ask that the tapes be deleted if they feel sensitive information was discussed during the session that they do not want the research team to hear.

4 - Study Objectives

4.1 Hypothesis

The refined PF strategy will result in a higher level of implementation fidelity of ALTA (primary outcome) and improved BP control and antihypertensive medication adherence (secondary outcomes) at 12 months, compared to a self-directed control arm.

4.2 Primary Objective

The primary objective of this study is to refine the practice facilitation (PF) strategies that will be tested in a cluster randomized trial, through a formative evaluation of the barriers and facilitators to implementation of the ALTA intervention based on the Consolidated Framework for Implementation Research and input from a Steering Committee.

4.3 Secondary Objectives (if applicable)

5. To test the hypothesis that the refined PF strategy will result in a higher level of implementation fidelity of ALTA (primary outcome) and improved blood pressure (BP) control and antihypertensive medication adherence (secondary outcomes) at 12 months.
6. To explore potential moderating factors at the practice and individual levels (e.g., organizational capacity to change, evidence-based practice attitudes) that influence implementation of ALTA in a network of 10 safety-net primary care practices in New York.

4.4 Tertiary Objectives

7. To evaluate the impact of ALTA on the patient-provider relationship (i.e., relationship commitment, patient-provider trust, and patient anxiety in the interaction)
8. To determine whether changes in patient-provider relationship that result from ALTA are associated with changes in medication adherence and BP control (secondary outcomes)

5 - Study Design

5.1 General Design

Using a stepped-wedge cluster randomized control trial design, this study will evaluate the effect of a tailored PF strategy on the implementation of Advancing Long-term Improvements in Hypertension Outcomes through a Team-based Care Approach (ALTA), our systems-level approach to improving medication adherence and BP control, among patients with uncontrolled HTN receiving care in 10 safety-net practices in New York.

Using a mixed-methods approach, this study will be conducted in two phases: (1) a pre-implementation phase where we will refine the PF strategy, based on the Consolidated Framework for Implementation Research (CFIR) to facilitate implementation of ALTA at the practices and (2) an implementation phase, guided by Proctor's Implementation Outcomes Framework (IOF). The primary aim of the implementation phase is to evaluate, in a stepped-wedge cluster randomized trial, the level of implementation fidelity (e.g., degree to which a program is delivered, as intended) of ALTA because of the tailored PF strategies. The secondary aims are to compare the effects of PF versus usual care (UC) on BP control and medication adherence in 10 safety-net primary care practices and patients with uncontrolled HTN who are non-adherent to their antihypertensive medications. We will also explore the potential moderating factors at the practice and individual levels (e.g., organizational capacity to change, evidence-based practice attitudes) that influence level of implementation fidelity of ALTA at the practices. We will also explore the impact of ALTA on the patient-provider relationship (i.e., relationship commitment, patient-provider trust, and patient anxiety in the interaction), and determine whether any changes to the relationship also affect patients' BP control and medication adherence.

As shown in Figure 1, each participating practice will start with the UC phase and are block-randomized into four waves, with two sites per wave. The UC phase will be followed by the pre-implementation phase of 6 months, during which facilitators will conduct a practice evaluation (e.g., workflow analysis, environmental scan) based on CFIR, refine the PF strategies that will be used in the implementation phase, and train staff in the ALTA model. Following this period, sites will implement ALTA with the assistance of the facilitator for 12 months, with a 3-month follow-up period for outcome assessment.

Figure 1. Stepped wedge design of ALTA implementation

Cohort	Implementation															
	Year 1				Year 2				Year 3				Year 4			
	3	6	9	12	3	6	9	12	3	6	9	12	3	6	9	12
1		UC	Pre-Imp		Intervention				OE	FU						
2		UC		Pre-Imp		Intervention				OE	FU					
3		UC			Pre-Imp		Intervention				OE	FU				
4		UC				Pre-Imp		Intervention				OE	FU			
5		UC					Pre-Imp		Intervention				OE	FU		

5.1.1 Study Duration (if applicable)

The study duration is 24 months. During the UC phase, patients at the sites will receive standard HTN care delivered by their primary care providers for the first 3 months. The pre-implementation phase will be the following 6 months of the trial to refine the PF strategy that will be used during the implementation phase. The implementation phase will be 12 months and there will be two study visits: consent/baseline and 12-month follow-up.

5.1.2 Number of Study Sites

The study will be conducted at the network of 10 safety-net practices in New York.

5.2.1 Primary Outcome Variables

The primary outcome measure is the level of implementation fidelity of ALTA at the practices. Implementation fidelity is defined as the degree to which an intervention was delivered, as intended by program developers. We will use a mixed methods approach to assess the five core domains of implementation fidelity defined by Proctor's IOF: (1) adherence to the program protocol; (2) dose of the program delivered; (3) quality of program delivery; (4) participant responsiveness; and (5) program differentiation.

5.2.2 Secondary and Tertiary Outcome Variables (if applicable)

Secondary outcomes will be measures of clinical effectiveness—BP control and adherence to antihypertensive medications at the pre-intervention (baseline) and post-intervention (12 month) periods.

BP control, the major secondary outcome, will be defined as SBP <140 and DBP <90 mmHg. BP control will be assessed using the mean of the last two measurements recorded in the EHR during each of the pre-intervention and post-intervention study periods (baseline and 12 months). BP readings will be extracted from patients' EHR by trained RAs. We will use the last two recorded measures to reduce variability associated with multiple BP measurements being taken by different clinic staff. We will also examine the proportion of patients with BP control <130/80 mmHg in exploratory analyses to provide preliminary data on BP control rates of hypertensive patients when considering the new guidelines. We will also explore mean change in systolic and diastolic BP based on the mean of the last two recorded BP readings in the EHR during the pre- and post-intervention periods.

Medication adherence will be assessed via pharmacy refills obtained from prescription orders in the clinic EHR using the proportion of days covered (PDC) metric. The PDC is calculated as the total number of days covered by the medication divided by the number of days between the first fill of the medication in the study period and the end of the study period. Thus, as opposed to other pharmacy refill metrics, the PDC accounts for non-persistence with medications by tracking medications during the study period despite early discontinuation. We will count the days the patient was covered by each of their prescribed antihypertensive medications based on the prescription fill date and days of supply. If prescription fills for the same medication overlap, then we will adjust the prescription start date to be the day after the previous fill has ended. Patients will be considered adherent if

they fill $\geq 80\%$ of their antihypertensive medications over the 12 months. In addition, we will assess the extent of medication non-adherence and the associated reasons based on the survey developed by [name].

Tertiary outcomes will include measures of the patient-provider relationship- relationship commitment, patient-provider trust, patient anxiety in the interaction, patient trust in healthcare, discrimination in medical setting, Health literacy, health intake, and patient trust in medical technology at the pre-intervention (baseline) and post-intervention (12 month) periods.

Relationship commitment: In this study, we operationalize relationship commitment as patients' commitment to maintain care with their PCP when ALTA is introduced into their site. To assess patients' *perceived commitment* to their PCP, we will utilize the self-report measure developed by Berry et al. in a sample of primary care patients. The 5-item measure asks patients to rate their degree of commitment to the relationship with their doctor on a 7-point Likert scale (*strongly disagree* to *strongly agree*). Sample items include: *The relationship with my doctor is...something I am committed to; something I care about; and important to me.* To assess the *behavioral and affective indicators* of relationship commitment we will use natural language processing (NLP) and analyze text of patient-provider interactions that occur in the 12 months prior to ALTA, and over the 12 months ALTA phase. Data will be extracted from the EHR (e.g., clinical notes, messages, and free text) and MyChart to conduct these analyses.

~~Patient anxiety in the interaction; will be measured using the 6-item State Anxiety Inventory (STAI-6), which has been used to measure state anxiety (anxiety about an event) in patient-provider visits in prior research. Items are rated on a 4-point scale (almost never to almost always) and include: “I am comfortable; I am at ease” and “I feel nervous.” The STAI-6 is written at a 6th-grade reading level and available in Spanish ($\alpha=0.86$ to 0.95). We will also apply text analysis to the transcribed patient-provider visits to identify the expression of patient anxiety in the interaction.~~

Health literacy will be assessed using the validated Short Assessment of Health Literacy from the PhenX toolkit. The 18-item measure is available in English and Spanish ($\alpha=0.89$ and 0.80 , respectively). Digital and health literacy plays an influential role in how well patients are able to engage with providers, especially through digitally-mediated communications when English is not their first language.

Equity will be assessed using the validated Discrimination in Medical Settings Scale. Power differentials between patient and provider that can be exacerbated due to technology. When relationships are perceived as equitable, individuals are more likely to display behaviors that reinforce relationship commitment, and report that their partner is also engaging in them.

We will be assessing patients experience with technology using the Tech In Take Survey.

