The secondary outcomes will be measures of clinical effectiveness—BP control and adherence to antihypertensive medications at the pre-intervention (baseline) and post-intervention (12 month) periods.

The tertiary outcomes will be measures of the patient-provider relationship – relationship commitment, patient-provider trust, and patient anxiety in the interaction– at the pre-intervention (baseline) and post-intervention (12 month) periods.

Study Duration

The study duration is 5 years. The pre-implementation phase will be 9 months and the implementation phase will be the remaining 4 years. Sites and participants enrolled in the

implementation phase will participate in the trial for 15 months. The approximate start date for the trial is September 1, 2018. The approximate end date is November 30, 2027.

Study Design

Using a mixed-methods design, the proposed study will be conducted in two phases: 1) A pre-implementation phase (surveys, QI interviews) and 2) an implementation phase.

For the pre-implementation phase, we will use a mixed methods observational research design to refine the PF strategies that will be tested in the implementation phase.

For the implementation phase, we will evaluate, in a stepped-wedge cluster randomized controlled trial, the effect of the PF strategy on the level of implementation fidelity (primary outcome) of ALTA, as well as on clinical outcomes (secondary outcomes) and the patient-provider relationship (tertiary outcomes) as compared to usual care at 12 months.

Study Population

The study population will include practice clinical and nonclinical staff and patients with uncontrolled hypertension (HTN) receiving care in the network of 10 safety-net primary care practices in New York.

Patient Eligibility Criteria

Inclusion Criteria:

- Be fluent in English or Spanish
- Be age 18 years or older
- Receiving care at one of the 10 safety-net primary care practices
- Have uncontrolled HTN documented in the electronic health record (EHR) on at least two visits in the past year (defined as an average BP \geq 140/90 mmHg)
- Have been prescribed at least one anti-hypertensive medication and be non-adherent to their medications, defined as adherence $<80\%$ in the preceding 12 months, as determined by prescription orders obtained from the clinic EHR.

Exclusion Criteria:

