Adherence to antihypertensive medications (secondary outcome)	
 Proportion of days covered metric based on pharmacy refill data EHR 	
 EHR Voils Adherence Measure 	Baseline and 12 months
Patient-provider relationship	
 Perceived strength of relationship commitment Level of mutual trust between patients and providers Level of patient anxiety in the interaction 	
 EHR MyChart Survey 	Baseline and 12 months (survey) Ongoing (EHR and MyChart)
Semi-structured interviews			
Exit interview	
 Moderator's guide that inquiries about satisfaction and recommendations for improvements as well as impacts of ALTA on the patient-provider relationship 	
 Interviews with 30 clinical and nonclinical staff across all sites Interviews with 30 patients across all sites 	12 months

An outcomes assessment is completed at the Implementation Phase Study Visit at 12-months, including surveys about satisfaction with the intervention and implementation process at each site. A set of questions measuring potential ripple effects and capacity for sustainability will be assessed at this time at FGP practices as part of the 12-month Online Survey, and is described below. We are completing these questions at FGP practices only to understand sustainability considerations within these practices. Questions take less than 10 minutes to complete.

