6.3.6 End of Study and Follow Up

Patient Consent at baseline: During this visit, trained RAs will use a standardized form to screen patients based on the study's inclusion and exclusion criteria. Verbal consent will be obtained prior to beginning the eligibility screening. Only patients that meet all eligibility criteria will then complete the consent procedures, during which a trained RAs will describe the study in easy-to-understand language. If the patient remains interested, the RA will obtain written informed consent in the patient's preferred language (English or Spanish). The patient will then complete a demographic questionnaire, validated surveys on patient trust, relationship commitment and anxiety, and have their medical chart reviewed by a trained RA. This visit should take 15 minutes.

Final study visit at 12-Months (post randomization): At 12 months, trained RAs will repeat the chart review procedures for consenting patients, in accordance with IRB and

HIPAA regulations. Patients will also complete the same measures on patient trust, relationship commitment and anxiety. In addition, we will conduct semi-structured interviews with a random sample of 30 patients with uncontrolled HTN about their experiences with ALTA over the past 12 months and its impact on the patient-provider relationship, as well as recommendations for improvements. This visit will take approximately 60 minutes.

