Maximum likelihood estimation of mixed-effects models will be used to account for missing data; this is equivalent to an assumption of data missing at random. We will conduct sensitivity analyses assessing this assumption. We will also compare participants with and without missing values in baseline and site characteristics, as well as intervention vs control group status; if differential patterns emerge, we will consider using multiple imputation and/or inverse probability weighting to adjust for missing data. For our behavioral measures of commitment and trust derived from text analysis, we will use Python with a dedicated suite of libraries for sentiment analysis and emotion detection. The text processing libraries will be used to complete the pre-processing steps including tokenization, stemming, and lemmatization. Tokenization is the process of separating text into smaller units, i.e., words, characters, or subwords. Stemming and lemmatization will be done to reduce inflectional forms and derive the common base form [e.g., am, are, is → be]. Next, each document (clinical notes, transcripts, secure messages) will be represented as vectors using word embeddings. Distributional semantics models (e.g., continuous Bag-of-Words, Skip-gram, Global vectors) will be used to represent each word as a vector while preserving the contextual information of the word before the training phase. Resources such as lexicons (e.g., LIWC, EmoLex) will be used for feature extraction representing presence or absence of emotion words, and words associated with opening or closing rituals of a conversation. Next, multiple supervised and unsupervised algorithms (e.g., attention-based neural models, transformers architecture) will be trained on the dataset and an optimized model will be established via several rounds of experiments and rigorous evaluations. Once the best fitting model is established, it will be used to train on clinical notes data before and after ALTA implementation. Patient and providers' sentiment will be compared to establish how the relationship has changed through ALTA participation. we will use GLMM to analyze the effect of ALTA on the tertiary outcomes of patient state anxiety, SBP, DBP, and PDC. Since each individual outcome is of interest, testing will be 2-sided with a Type I error rate of 0.05 and no adjustment for multiple testing.

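### Patient anxiety is still scheduled and tested although its only instrument is struck out, and three other tertiary outcomes have a scale but no visit, table row or analysis

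*Combined protocol and SAP*

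**What the plan says.** **Anxiety.** The tertiary objective in 4.4 reads "To evaluate the impact of ALTA on the patient-provider relationship (i.e., relationship commitment, patient-provider trust, and patient anxiety in the interaction", and the Synopsis names the same three constructs as tertiary outcomes: "relationship commitment, patient-provider trust, and patient anxiety in the interaction". Section 5.1 repeats them. Section 5.2.2 then gives the instrument, "Patient anxiety in the interaction; will be measured using the 6-item State Anxiety Inventory (STAI-6", and a second measure, "We will also apply text analysis to the transcribed patient-provider visits to identify the expression of patient anxiety in the interaction". Both sentences sit in one paragraph that is marked as struck out.

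The rest of the plan still relies on anxiety. Table 2 in 6.1.4 lists "Level of patient anxiety in the interaction" without naming a scale. At baseline, 6.3.6 has patients complete "validated surveys on patient trust, relationship commitment and anxiety", and it repeats those measures at 12 months. Section 6.4.3.3 states that "we will use GLMM to analyze the effect of ALTA on the tertiary outcomes of patient state anxiety, SBP, DBP, and PDC", two-sided at 0.05 with no adjustment for multiple testing.

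**Other tertiary outcomes.** Section 5.2.2 adds "patient trust in healthcare, discrimination in medical setting, Health literacy, health intake, and patient trust in medical technology" to the tertiary list, all at baseline and 12 months, and names a scale for each in the paragraphs that follow.

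**Visit lengths.** The patient consent/baseline visit is 30 minutes in 6.3.1 and 15 minutes in 6.3.6. The 12-month patient visit is 75 minutes in 6.3.1 and 60 minutes in 6.3.6.

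**The concern.** An outcome needs four things to be reportable: a definition with an instrument, a collection time, a place in the data-collection schedule, and an analysis. For tertiary outcomes the plan breaks this chain in two opposite ways. Anxiety has the schedule and the analysis but no live instrument. Discrimination, health literacy and technology intake have an instrument and a stated time but no schedule entry and no analysis.

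At stake is which tertiary results are collected, tested and claimed. Section 7.5.1 points to Table 2 for each measure and its timing. Staff working from Table 2 and 6.3.6 would look for an anxiety survey that the plan no longer specifies, and would not be told to give the other scales. An analyst working from 6.4.3.3 would be asked for an anxiety effect with no defined score, and would find no model for outcomes that 5.2.2 promises. The second tertiary objective, which relates change in the patient-provider relationship to adherence and BP control, inherits the gap in its anxiety part.

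**Working it through.** No arithmetic beyond counting applies. Each of the eight tertiary outcomes listed in 5.2.2 was traced through the later sections.

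| Outcome in 5.2.2 | Instrument in 5.2.2 | Instrument in 6.1.4 text | Table 2 | Patient visits, 6.3.6 | Analysis, 6.4.3.3 |
|---|---|---|---|---|---|
| Relationship commitment | 5-item scale, text analysis | Yes | Yes | Yes | Yes |
| Patient-provider trust | Patient and provider trust scales, text analysis | Yes | Yes | Yes | Yes |
| Patient anxiety | STAI-6 and text analysis, both struck out | None | Yes, no scale | Yes, both visits | Yes, GLMM |
| Discrimination | Discrimination in Medical Settings Scale | None | No | No | No |
| Health literacy | Short Assessment of Health Literacy | None | No | No | No |
| Health intake | Apparently the Tech In Take Survey | None | No | No | No |
| Trust in healthcare | Patient Trust in Healthcare Practice Scale | None | Not named | Not named | Not named |
| Trust in medical technology | Patient Trust in Medical Technology Scale | None | Not named | Not named | Not named |

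**Anxiety.** The only other live text measure that mentions anxiety is in the 6.1.4 table of commitment behaviours. There, absence of anxiety words is one marker of relationship commitment, not an anxiety outcome, so it does not fill the gap.

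**The two extra trust scales.** Section 5.2.2 says they assess commitment and trustworthiness. Table 2 lists commitment and mutual trust by construct, 6.3.6 refers to patient trust and commitment in general terms, and 6.4.3.3 models both constructs. The two scales may therefore be meant there, although 5.2.2 lists them as outcomes separate from patient-provider trust.

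**Health intake.** The outcome list and the instrument paragraph use different names. That they are the same measure is an inference from position and elimination.

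**Count.** 2 traceable throughout + 1 tested without a live instrument + 3 with an instrument but no schedule entry or analysis + 2 ambiguous = 8. The traceable number is 2 on the strict reading and 2 + 2 = 4 on the generous one.

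**Visit lengths.** 30 − 15 = 15 minutes apart at baseline; 75 − 60 = 15 minutes apart at 12 months. Neither figure can be checked against the survey content while that content is unsettled.

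**Model.** Section 6.4.3.3 names Poisson regression for the relationship outcomes while calling commitment continuous and trust ordinal. Any scale added to that section therefore cannot simply borrow the stated model.

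**The case against.** **The strike-out may not be real.** It is known only from marks in text that a program read from PDF. If they are an artefact or leftover redlining, the STAI-6 is in force and the anxiety defect shrinks to an omission from 6.1.4. This stands as a caveat. It does not remove the point: the absence of any anxiety instrument in 6.1.4 agrees with a deletion, and on either reading one part of the current text has to change.

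**All five added outcomes are missing.** A reader might infer this. The documents do not support it for the two trust scales, which can be read as covered by construct. Only three are absent on any reading.

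**Baseline data are lost for up to 1,000 patients.** A reader might add the 700 ALTA patients and 300 controls and reach this. It is not established. Section 5.2.2 does state baseline and 12 months for all eight outcomes, so the fault is that 6.3.6 and Table 2 do not match it. The REDCap survey build is not shown. Section 6.3.4 also speaks of approximately 500 patients, and the plan does not say when the STAI-6 was struck or the other scales added. The same section draws the sample from patients already exposed to ALTA, while 6.1.1 places baseline collection in usual care. A pre-exposure baseline is thus in doubt for every tertiary outcome, not only these.

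**These outcomes are tertiary.** Section 5.1 presents this aim as exploration. That stands, and it limits the weight of the point.

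**Conclusion.** The contradiction is real and confined to tertiary outcomes. As extracted, the plan commits to a two-sided 0.05 test of patient anxiety with no measure in force. It also promises three outcomes at two time points that its measures table, patient visits and analysis never mention. Two more scales need a clear place.

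It would go too far to say that an anxiety result can never be produced, since STAI-6 data may have been collected before the deletion and the deletion itself is read from extraction marks. The number of patients affected cannot be determined from the documents. Implementation fidelity, BP control and medication adherence as outcomes are untouched. This should be corrected because it decides which tertiary effects are collected and claimed, but it does not threaten the main results.

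**What to change.** 1. **Decide on anxiety.** Either remove it from the Synopsis, 4.4, 5.1, 5.2.2, Table 2, 6.3.6 and 6.4.3.3, or reinstate the STAI-6 as live text in 5.2.2 and add it to 6.1.4. If it is removed, state the date and reason and report any STAI-6 data already collected, so that a prespecified outcome does not disappear silently.
2. **Carry one list.** Make the outcome list in 5.2.2, Table 2, the visits in 6.3.6 and the analysis in 6.4.3.3 agree. Name each retained scale, including the two extra trust scales, give its visit or visits, and label it exploratory outcome, covariate or moderator. Remove any scale that is not retained from the outcome list. Use one name for health intake and the Tech In Take Survey.
3. **Name a suitable model.** Analyse retained score outcomes with a mixed model for a continuous score, not the Poisson model now in 6.4.3.3.
4. **Reconcile the visit lengths** in 6.3.1 and 6.3.6 (30 against 15 minutes; 75 against 60 minutes) once the list is settled.

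The cost is protocol and SAP wording and, where needed, the REDCap survey list; the scales are already chosen. The downside is a somewhat longer survey or fewer stated outcomes.
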